## 7 DATA HANDLING METHODS

## 7.1 Visit Windows

All information will be listed, summarized, and analyzed according to the nominal visit. No visit windowing will be performed.

## 7.2 Data Presentation

Individual subject data listings will be provided to support summary tables and serve as a data source. Unless otherwise noted, all data collected during the study for subjects in the Randomized population will be included in data listings. No imputation, other than the imputation of desensitization response and MTD at Exit DBPCFC as described in Sections 7.3 and 7.4, will be included in listings. Listings will be sorted by treatment group, subject identifier, and visit date (where applicable). If a listing includes screen failures, they will be listed as treatment group 'NONE' and sorted after all randomized subjects.

Visit 02 and Updosing Week 12 will be combined for by-visit summaries. If a subject has a non-missing result recorded for both Visit 02 and Updosing Week 12 visits, the result from the assessment closest to the midpoint between the Updosing Week 10 and Updosing Week 14 visit will be summarized. If there is no Updosing Week 14 visit, the assessment closest to 14 days after the Updosing Week 10 visit will be used. If there is a tie, the Updosing Week 12 assessment will be used. This visit will be displayed as "Visit 02/ Updosing Week 12."

Unscheduled visits will be listed but not included in by-visit summaries. Results from unscheduled visits may be used as baseline values, and for other derivations not tied to visit names (for example, unscheduled visits are included in the determination of worst post-baseline values for physical examination results).

#### 7.3 Maximum Tolerated Dose at DBPCFCs and Escalation Failures

The MTD for a DBPCFC is defined as the maximum single dose of peanut protein resulting in no more than mild symptoms and assessed by the investigator to have been tolerated (i.e., subject did not experience any dose-limiting symptoms). The MTD at the Screening DBPCFC will be used as the baseline amount of peanut protein tolerated. If a subject is administered non-standard doses at DBPCFC (i.e., other than the doses listed in Tables 3.1 or 3.4), the MTD will be considered the highest tolerated standard dose (i.e., 3 mg, 10 mg, 30 mg, 100 mg for either DBPCFC; 300 mg for Exit DBPCFC) which is tolerated.

An escalation failure is a subject who does not reach the target 300 mg/day dose by Week 34, or fails to complete at least a 2-week maintenance at that dose level.

Where necessary, desensitization response and MTD at the Exit DBPCFC will be imputed for subjects who do not have an Exit DBPCFC as shown in Table 7.1. As a general rule, subjects who do not undergo an Exit DBPCFC for any reason will be categorized as desensitization non-responders; and the imputed value for their MTD will be the maximum dose of peanut protein they tolerated in their Screening DBPCFC. The one exception to this rule is in the event of documentation that a subject introduced ad libitum peanut consumption into their diet and tolerated amounts of peanut exceeding a single peanut kernel (the targeted level of desensitization in the study). Although subjects are repeatedly and strenuously admonished, per protocol, to maintain a peanut-avoidant diet, there is always the potential for the admonishments to go unheeded, as well as for accidental exposure. In the unlikely event that a subject starts to consume peanut ad libitum before exiting the trial, whether or not this occurs as the result of a protocol violation, provision has been made for imputing their results (see Table 7.1). If, however, the amount of peanut consumed and tolerated by a subject claiming ad *libitum* peanut consumption cannot be ascertained from the eCRF or source documentation, then the subject will be classified as a non-responder who missed their Exit DBPCFC after having discontinued for reasons unrelated to treatment. If a subject added ad libitum peanut consumption to their diet and had additional reasons for missing the Exit DBPCFC, then the imputation rules for ad libitum

peanut consumption will be determined during blinded data review on a case-bycase basis.

Classification of responder and non-responder categories and subcategories, and reasons for missing the DBPCFC will be determined during blinded data review prior to database lock and unblinding, as described in Section 12.

Response Subcategory for subjects missing Exit DBPCFC [1]	Reason for missing Exit DBPCFC	Imputation Rule for Desensi- tization Response	Imputation Rule for MTD at the Exit DBPCFC	Justification
Ad libitum peanut consumption	Added ad libitum peanut consumption to their diet	Responder, provided there is sufficient documentation for a peanut kernel or greater [4]	300 mg, provided there is sufficient documentation for a peanut kernel or greater [4]	Documentation available that the subject achieved at least the minimum targeted level of desensitization
Reached 300 mg/day target but DBPCFC not conducted	
 
Eligible for DBPCFC but it was not conducted due to at least one treatment-related reason, as entered on the eCRF [2]
 
Eligible for DBPCFC but it was not conducted only for reasons unrelated to treatment, as entered on the eCRF [2]
 
	Non-responder	MTD at Screening DBPCFC	Unable to verify desensitization
Escalation failure	
 
Fail to achieve the target maintenance study product dose of at least 300 mg/day and thus did not qualify for the Exit DBPCFC.
 
Reasons include:
 
Discontinued as an escalation failure during initial escalation (Visit 01) [3]
 
Discontinued as an escalation failure during up-dosing prior to Week 24 [3]
 
Discontinued as an escalation failure after Week 24 [3]
 
Discontinued for treatment- related AE or death [3]
 
Discontinued for reasons related to treatment [3]
 
Discontinued for reasons unrelated to treatment [3]
 
	Non-responder	MTD at Screening DBPCFC]	Unable to verify desensitization

Table 7.1 Imputation Rules for Desensitization Response and MTD

[1] Subjects will be assigned to only one response subcategory during blinded data review.

[2] More than one reason may be given for the DBPCFC not being conducted for a subject who reached the 300 mg/day target. Each reason will be classified as treatment-related, or not, during blinded data review.
[3] More than one reason for discontinuation may be given. Each discontinuation reason will be classified as treatment-related, or not, during blinded data review. Escalation failure is a specific reason for early discontinuation on the eCRF.

[4] Information from free text fields on the eCRF for protocol deviations or reason for early discontinuation will be used to determine the imputed value. If it is clear that an amount of peanut exceeding a single peanut kernel was regularly consumed without eliciting symptoms, then a value of 300 mg will be imputed. If the amount of peanut consumed cannot be ascertained or is less than the equivalent of a peanut kernel, then the subject will be classified as a Non-responder and no value will be imputed.

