## **3.2 Schedule of Study Assessments**

## 3.2.1 Screening Period

The screening visits (Visit 00) may occur over several days, and will include an initial DBPCFC. The DBPCFC will have both a peanut challenge and a placebo challenge, using up to 100 mg (143 mg cumulative) each of peanut protein and placebo, based on the PRACtical issues in ALLergology Joint United States/European Union Initiative (PRACTALL) dosing regimen, as shown in Table 3.1. At the investigator's discretion, a 1 mg dose may be added at the beginning of the escalation.

Challenge Doses					
	Peanut flour with				
Peanut Protein	50% protein content				
(mg)	(mg)				
3	6				
10	20				
30	60				
100	200				

Table 3.1. PRACTALL Screening DBPCFC Dosing Schedule

A DBPCFC is conducted either as two challenges during a single day visit (with at least 3 hours separating the two halves of the challenge) or over 2 days with the placebo challenge on one day and the peanut challenge on the other day. The food challenges are presented in random order and are performed under double-blind conditions.

Subjects who have dose-limiting symptoms at or before the 100 mg dose of peanut protein will be enrolled into the study. Those who successfully consume a dose of 100 mg of peanut protein during the Screening DBPCFC, without experiencing dose-limiting symptoms, will be considered screen failures and will not be randomized. Any subject who is assessed to have had dose-limiting symptoms to both parts of the Screening DBPCFC (i.e., to placebo [oat flour] as well as peanut flour) will be considered to be a screen failure and will not be randomized.

Subjects who meet eligibility criteria will return for a baseline visit, which may occur over multiple days. See Table 3.5 for the schedule of assessments.

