## 3.2.3 Exit Visit (Visit 03)

After approximately 24 weeks of randomized study treatment, eligible subjects who reach the targeted daily dose of 300 mg/day and maintain that dose for 2 weeks will undergo an Exit DBPCFC of up to 600 mg (1043 mg cumulative) peanut protein and placebo (see Section 6.6.2 of protocol). Subjects who have not reached 300 mg/day by Week 24 will continue to up-dose as tolerated until they are eligible for the Exit DBPCFC (after 2 weeks of at-home dosing with 300 mg/day). The Exit DBPCFC will be conducted in a manner similar to the Screening DBPCFC but with the dosing schedule as shown in Table 3.4. Note also that subjects are not scheduled for a dose of study product at home or in-clinic on the day of Visit 03.

Subjects who fail escalation, whose dose escalation is halted, and/or who prematurely discontinue treatment, will return to the site for an Early Discontinuation visit that consists of the same procedures as the Exit visit, but without a DBPCFC or associated optional blood draws. An Early Discontinuation visit is to occur 14 days from the last dose of study product.

Table 3.4. PRACTALL Exit DBPCFC

Challenge Doses					
	Peanut flour with				
Peanut Protein	50% protein content				
(mg)	(mg)				
3	6				
10	20				
30	60				
100	200				
300	600				
600	1200				

The schedule of study assessments will be as follows:

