#### 5.4 Intent-to-Treat (ITT) Population

The ITT population will consist of all randomized subjects who received at least one dose of randomized study treatment. Subjects will be analyzed according to randomized treatment. The ITT population will be used as the primary analysis population for all analyses of efficacy endpoints.

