## 9.3 Secondary Efficacy Analyses

All secondary analyses of key secondary endpoints will be performed in the ITT population.

The key secondary efficacy endpoints are:

- Peanut MTD at the Exit DBPCFC
- Change from baseline in the Peanut MTD at the Exit DBPCFC.

These will be tested in a hierarchical order. If the primary efficacy analysis is significant at the 0.05 level, then the MTD at Exit DBPCFC will be tested with a Type I error rate of 0.05. If this test is significant, then change from baseline in MTD at the Exit DBPCFC will be tested with a Type I error rate of 0.05. This closed testing procedure maintains the overall Type I error rate at 0.05. If the first test is not significant, the p-value for the change from baseline will be displayed for informational purposes only.

Sensitivity analyses of the key secondary efficacy analyses will be performed by excluding subjects with an indeterminate DBPCFC, as defined in Section 9.2, prior to performing the analyses on the ITT population. Analysis of key secondary endpoints will also be repeated in the mITT and PP populations as sensitivity analyses.

DBPCFC results will be listed at both time points, where applicable, for all randomized subjects. Screening DBPCFC results will be listed for screen failures. Composite results, including MTD and maximum symptom (defined as the most severe of any recorded symptom for that food challenge), will be listed for each DBPCFC for all enrolled subjects, including screen failures. Indeterminate results will be indicated.

The peanut MTD at Screening and Exit DBPCFCs, last dose achieved, number of days at last dose (excluding any time at that dose level prior to an escalation or deescalation, and excluding any time after an Exit DBPCFC), and whether the subject was an escalation failure (per Tables 7.1 and 7.2) will also be listed. Imputed peanut MTD at the Exit DBPCFC will be flagged. Desensitization response status and response subcategories for missed Exit DBPCFC and desensitization response will also be listed, as described in Section 7.3.

Dose levels administered during DBPCFCs will be summarized by time point and food challenge, by treatment group and overall for the Randomized and ITT populations.

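### SAP 7.3's list of standard doses for challenges with a non-standard dose omits 600 mg and 1 mg, and no analysis value is set for a subject who tolerates no Screening dose, so MTD can be mis-scored or undefined in both key secondary analyses

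*SAP*

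**What the plan says.** SAP 7.3 first gives a general definition: MTD is the largest single dose of peanut protein that causes no more than mild symptoms and that the investigator judges tolerated. It then adds a fallback for challenges with non-standard doses, meaning doses "other than the doses listed in Tables 3.1 or 3.4". In that case MTD is the "highest tolerated standard dose (i.e., 3 mg, 10 mg, 30 mg, 100 mg for either DBPCFC; 300 mg for Exit DBPCFC").

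Other sections bear on this rule:

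- **Top Exit dose.** Section 3.2.3 plans an "Exit DBPCFC of up to 600 mg (1043 mg cumulative) peanut protein and placebo". Table 3.4 lists 600 mg, and 9.3.1 places it on the log10 scale.
- **Optional 1 mg.** Under 3.2.1 (and Protocol 6.6.1), "a 1 mg dose may be added at the beginning of the escalation" at Screening. Neither Table 3.1 nor Table 3.4 lists it. Section 9.3.1 speaks of an optional 1 mg dose at Exit as well and starts every subject at a 1 mg level. Section 9.3.2 names 1 mg as one of the baseline MTDs at which results are reported if slopes differ.
- **Eligibility.** "Subjects who have dose-limiting symptoms at or before the 100 mg dose of peanut protein will be enrolled into the study" (3.2.1). No minimum tolerated dose is required.
- **Floor.** Section 9.3.1 assigns 0.3 mg to subjects who cannot tolerate the lowest Exit dose, so that a logarithm can be taken. No counterpart is given for Screening.
- **Imputation.** For a subject without an Exit challenge, "the imputed value for their MTD will be the maximum dose of peanut protein they tolerated in their Screening DBPCFC" (7.3), with an exception for documented ad libitum peanut consumption.
- **Status of the endpoints.** If the primary test is significant, "then the MTD at Exit DBPCFC will be tested with a Type I error rate of 0.05"; change in MTD follows in the hierarchy (9.3). "The ITT population will be used as the primary analysis population for all analyses of efficacy endpoints" (5.4).

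**The concern.** The fallback has a foreseeable trigger, because the plan itself allows a dose that is in neither table. Once triggered, its list does not cover the range of doses that the challenges and the models use. At the top it stops one level short, so a subject who tolerates the highest Exit dose can be scored one level too low. At the bottom it cannot return 1 mg, although the models treat 1 mg as a level.

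The missing Screening floor is a separate gap. Log10 Screening MTD is a covariate in both key secondary models, is subtracted to form the change score, and supplies the Exit MTD when the Exit challenge is missed. A subject who reacts to the first Screening dose is eligible but has no value for any of these.

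At stake is the scoring of two alpha-controlled endpoints in a trial of about 50 subjects. If a blank has to be filled, or a 600 mg result re-read, the choice should already be on record before treatment codes are known.

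**Working it through.** **Reproducing the SAP's scale.** Using log10 of the dose ratios for 3, 10, 30, 100, 300 and 600 mg:

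- Steps: log10(10/3) = 0.523; log10(30/10) = 0.477; log10(100/30) = 0.523; log10(300/100) = 0.477; log10(600/300) = 0.301. Section 9.3.1 gives 0.477 to 0.523 and about 0.3.
- Floor: log10(3/0.3) = 1.000, the one unit stated in 9.3.1.
- Cumulative doses: 3 + 10 + 30 + 100 = 143; + 300 = 443; + 600 = 1043 mg. All agree with the plan.

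**Applying the rules as written.**

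| Subject | Rule that applies | MTD | log10 |
|---|---|---|---|
| Exit, standard doses only, tolerates 600 mg | general definition | 600 mg | 2.778 |
| Exit, 1 mg added, tolerates 600 mg | fallback list | 300 mg | 2.477 |
| Screening, 1 mg added, tolerates 1 mg only | fallback list | none on the list | none |
| Screening, tolerates no dose | general definition; no floor | none | log10(0) is undefined |
| As the previous row, no Exit challenge | imputed from Screening | none | none |

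The second row is wrong by 2.477 - 2.778 = -0.301. For the third row, the general definition without the fallback would give 1 mg (log10 = 0), and the 0.3 mg value would give -0.523, so the open choice is worth log10(1/0.3) = 0.523. If 1, 3 or 5 of 50 subjects had no usable baseline, the adjusted models would lose 2%, 6% or 10% of the ITT population.

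**Effect on the tested quantities.** The documents do not say how many subjects are affected, so ranges are shown. For 600 mg scored as 300 mg in k of 25 CPNA subjects, the mean log10 change falls by k × 0.301/25:

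- k = 1: 0.012
- k = 3: 0.036
- k = 5: 0.060

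A simulation was also run, with 1,500 trials per setting and 25 subjects per arm. From SAP Section 4: 3 per arm without an Exit challenge (set to Screening MTD), and 66.7% versus 25% of challenged subjects tolerating at least 300 mg. Assumed, because the documents give no distributions:

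- Screening MTD 3/10/30 mg at 30/40/30%.
- CPNA Exit MTD 10/30/100/300/600 mg at 5/8.3/20/26.7/40%.
- Placebo Exit MTD 0.3/3/10/30/100/300/600 mg at 8/15/17/20/15/20/5%.
- Exit MTD unrelated to Screening MTD.

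The models were ANCOVA of log10 change and complementary log-log discrete hazards, each with treatment and log10 baseline. The base case gave an ANCOVA contrast of 0.815 and a median hazard ratio of 0.293.

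- *600 mg scored as 300 mg, k = 1, 3, 5 CPNA subjects:* contrast -0.012, -0.036, -0.060; hazard ratio multiplied by 1.05, 1.17, 1.29. All are against CPNA.
- *First-dose Screening reactors dropped rather than set to 0.3 mg, 1, 3 or 5 of 50, otherwise like the rest:* mean shift in contrast -0.001, 0.000, -0.005 (95% range at 5: -0.197 to 0.206).
- *The same, but every CPNA reactor (1, 2 or 3 of them) also misses Exit:* contrast +0.079, +0.178, +0.281; hazard ratio multiplied by 0.91, 0.80, 0.69, toward CPNA.

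**The case against.** **600 mg.** The sentence in 7.3 defines non-standard by reference to Table 3.4, which lists 600 mg. By its own test 600 mg is standard, and only the parenthetical list leaves it out. Section 1 of the SAP records a change to the maximum Exit dose, so a list that was not updated is a plausible explanation (an inference). A careful programmer may well score 600 mg correctly. That stands as a reason to expect the right result, but the list is introduced as exhaustive and conflicts with the table. A reader might go further and infer that every 600 mg result is scored 300 mg. The documents do not support that, because the general definition returns 600 mg on the standard schedule.

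**1 mg.** A reader might infer that 9.3.1 contradicts itself, since a subject not given 1 mg who fails 3 mg counts as having passed 1 mg yet takes 0.3 mg. These are two uses: the hazards model needs the dose level failed, and the log scale needs a number. Nor does the gap require removing the 1 mg level, which 9.3.1 and 9.3.2 both use. At Screening, the choice between 1 and 0.3 mg was negligible in the simulation (5 CPNA subjects: mean contrast shift 0.000, hazard ratio × 1.00). What remains is that the 7.3 list cannot return a value the models provide for.

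**Screening floor.** The SAP does not say such subjects are dropped, and extending the 0.3 mg value is a natural reading. Section 9.3.1 also plans an estimate without the baseline term. However, the tested effect is the adjusted one, and the unadjusted estimate still needs an imputed Exit MTD when Exit is missed. The blinded review in Section 12 would see a blank in the MTD listing, but its case-by-case MTD rules cover only ad libitum peanut consumption. The addendum is silent.

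**Bias toward CPNA.** A reader might infer that the missing floor favours CPNA. That holds only if CPNA reactors also disproportionately miss Exit. The path is conceivable, since a subject who cannot tolerate 3 mg at Visit 01 is an escalation failure with no Exit challenge, but nothing in the documents shows that it occurs. The +0.281 figure is a one-sided worst case.

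**Conclusion.** The concern holds as a scoring gap in the two key secondary endpoints. The 7.3 list conflicts with Table 3.4 and 9.3.1 over 600 mg, and it cannot return the 1 mg value for which 9.3.1 and 9.3.2 provide. A subject who tolerates no Screening dose (or, under the fallback, only 1 mg) has no usable value in the adjusted ITT analyses of either endpoint unless a rule is added.

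The per-subject error is certain from the text: -0.301 log10 for 600 mg read as 300 mg. The effect on the trial is not, because the number affected is not given and may be zero. On the assumed distributions, 1 to 5 mis-scored CPNA subjects move the ANCOVA contrast by -0.012 to -0.060 from a base of about 0.82, against CPNA. Dropping first-dose reactors has no average effect if they resemble the rest.

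The primary endpoint is unaffected, since 300 mg and 600 mg both count as response and a subject without an Exit challenge is classified without reference to Screening MTD.

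**What to change.** Before unblinding, amend the SAP text:

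1. In 7.3, add 600 mg to the doses listed for the Exit challenge.
2. In 7.3, let the fallback return 1 mg when that dose was given and was the highest tolerated. This aligns it with 9.3.1 and 9.3.2, and the 1 mg level stays in the model.
3. Apply the existing 0.3 mg analysis value to subjects who tolerate no Screening dose, use it as their log10 baseline, and carry it into the imputed Exit MTD when the Exit challenge is missed.

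The cost is a few lines of text and no added analysis. The downside is that 0.3 mg is an arbitrary analysis floor, as it already is at Exit.

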The goal of this program is to induce a state of desensitization to peanut protein defined as the absence of moderate or severe reaction following ingestion of a specific dose of peanut protein. This state of desensitization should be sufficient to protect a subject with peanut allergy from an accidental exposure to a small amount of peanut protein while maintaining a peanut restricted diet. Protection to a whole peanut, approximately 250 mg of peanut protein (measured as 500 mg of peanut flour), would afford a meaningful level of clinical protection against accidental exposure to peanut protein, since accidental exposures are typically to only small amounts of the allergen.²³

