1.5 Rationale for the Dose Used for the DBPCFC

The study DBPCFC will be conducted in accordance with the recommended PRACTALL guidelines although the screening DBPCFC will not exceed the 100 mg (143 mg cumulative) dose to assess inclusion criteria, and the exit DBPCFC will not go above a 600 mg (1043 mg cumulative) dose to help ensure patient safety. Additionally, the DBPCFCs will progress through the dose levels in an unaltered sequence without repeating any dose.

The exit DBPCFC will assess protection against slightly more than 1 peanut's worth of peanut protein 300 mg (\geq 443 mg cumulative dose) since accidental exposures typically occur to limited amounts of allergen. To assess further desensitization, patients tolerating the 300 mg (443 mg cumulative) incremental dose will also be challenged with 600 mg (1043 mg cumulative), although not up to the 3000 mg dose (4443 mg cumulative), since at this point they will have been up-dosed only to the 300 mg dose level.

Since subjects are enrolled only if they are sensitive to ≤ 100 mg level (143 mg cumulative) peanut protein on the screening DBPCFC, this would represent a 10x increase in the incremental dose tolerated (and 10.3x increase in cumulative dose) which would be in line with the previous demonstration of a 10x total increase, although this was after treatment for 1 year, and to larger amounts of peanut protein. A DBPCFC started at a very low dose is conducted to confirm that spontaneous desensitization has not occurred.

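### SAP Table 7.1 and its footnote [4] give conflicting rules for ad libitum peanut eaters who miss the exit DBPCFC, and no planned test counts them as failures

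*SAP*

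**What the plan says.** SAP 7.3 makes every subject without an exit DBPCFC a non-responder, and "the imputed value for their MTD will be the maximum dose of peanut protein they tolerated in their Screening DBPCFC". It allows one exception: a subject documented to have taken up peanut ad libitum who "tolerated amounts of peanut exceeding a single peanut kernel (the targeted level of desensitization in the study").

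Table 7.1 implements the exception. Its response cell reads "Responder, provided there is sufficient documentation for a peanut kernel or greater", and its MTD cell imputes 300 mg on the same condition. Both cells cite footnote [4], which is worded differently. Its crediting branch requires clear evidence: "an amount of peanut exceeding a single peanut kernel was regularly consumed without eliciting symptoms, then a value of 300 mg will be imputed". Its other branch, which also takes in amounts that nobody can establish, applies where the intake "is less than the equivalent of a peanut kernel, then the subject will be classified as a Non-responder and no value will be imputed".

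Other places bear on the rule:

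- Table 7.2 lists ad libitum consumption as a responder subcategory and states no amount.
- Protocol 9.1.1 contains the exception, also without an amount.
- SAP 9.3.1 imputes the exit MTD under the 7.3 rules for all subjects with a missing exit DBPCFC.
- Protocol 1.1 gives the scale: "Protection to a whole peanut, approximately 250 mg of peanut protein (measured as 500 mg of peanut flour"). Protocol 1.5 adds: "The exit DBPCFC will assess protection against slightly more than 1 peanut's worth of peanut protein 300 mg".

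**The concern.** The rule decides the primary outcome of any subject it touches. Through the imputed MTD it also enters both key secondary analyses. Three things are wrong with it.

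1. The threshold is stated in two ways, and they disagree for a subject documented at exactly one kernel.
2. Footnote [4] leaves the MTD empty for a subject whom the rest of the plan gives a screening MTD. Read literally, that removes a known non-responder from the ITT analyses of MTD.
3. A responder credited on diet history has not passed the challenge that defines the endpoint. The plan reports how many there are by arm (SAP 9.1), but runs no test in which they count as failures.

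**Working it through.** **Threshold, side by side**

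| Place | Amount for credit | Exactly one kernel |
|---|---|---|
| SAP 7.3 text | more than one kernel, tolerated | non-responder |
| Table 7.1, both cells | one kernel or more | responder, MTD 300 mg |
| Footnote [4] | more than one kernel, regularly, without symptoms | in neither branch |
| Table 7.2; protocol 9.1.1 | none stated | not settled |

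The SAP gives no protein content for a kernel. If a kernel is taken as the protocol's whole peanut (an inference), one kernel is about 250 mg, and 250/300 = 83% of the endpoint dose.

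**MTD for an unknown or below-kernel amount**

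- SAP 7.3: both cases fall outside the exception, so the screening MTD applies. An unknown amount is also treated as a discontinuation unrelated to treatment, a Table 7.1 reason that carries the screening MTD.
- SAP 9.3.1: impute for every missing exit DBPCFC.
- Footnote [4]: no value.

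**Which analyses count a documented ad libitum subject as a failure?**

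- ITT: counted as a responder.
- mITT (5.5): kept, as a responder.
- PP (5.6): removed on premature withdrawal or a major deviation, not recoded.
- Completer (addendum 2.2): kept if eligible for the exit DBPCFC, otherwise removed.
- Indeterminate-challenge analysis (9.2): does not address a missing exit challenge.
- Section 11.4: changes MTD only, in the CPNA arm only, as a summary.

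None does.

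**The plan's own power first.** Inputs from SAP 4: 25 per arm, two-sided 0.05, and 25% placebo response among those challenged. CPNA response is 66.7% with 3 unchallenged per arm, or 70.75% with 5.

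- Effective rates: 0.25 × 22/25 = 22%; 0.667 × 22/25 = 58.7%; 0.25 × 20/25 = 20%; 0.7075 × 20/25 = 56.6%.
- Exact power under the SAP 9.1 test (Pearson, or Fisher if an expected count is below 5) is 80.0% and 80.2%. The stated figure of at least 80% reproduces.

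**Effect of one ad libitum responder.** The design rates already give unchallenged subjects no credit, so the subject is added to the design-rate responders. I enumerated two binomials for the challenged subjects, counted the unchallenged as failures, and then added one responder to one arm.

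| | 22 challenged, 66.7% v 25% | 20 challenged, 70.75% v 25% |
|---|---|---|
| Power, subject counted as a failure | 0.816 | 0.830 |
| Power, CPNA subject credited | 0.888 | 0.901 |
| P(significance lost when the CPNA subject is a failure) | 0.072 | 0.071 |
| Power, placebo subject credited | 0.717 | 0.728 |
| P(significance gained when the placebo subject is a failure) | 0.099 | 0.102 |

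The first row exceeds 80% because the number unchallenged is fixed here, not random.

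Examples, responders out of 25 (CPNA v placebo):

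- Borderline, CPNA subject: 13 v 6 (p = 0.041) becomes 12 v 6 (p = 0.077).
- Borderline, placebo subject: 13 v 7 (p = 0.083) becomes 13 v 6 (p = 0.041).
- Near the design means: 16 v 6 (p = 0.004) or 15 v 7 (p = 0.023) becomes 15 v 6 (p = 0.010), and nothing flips.

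**Effect on MTD.** The credit is log10(300/screening MTD). Assumed screening MTDs of 30, 10 and 3 mg give 1.00, 1.48 and 2.00 log10 units for that subject. Divided by 25, the arm mean moves by 0.04, 0.06 or 0.08.

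**The case against.** The strongest reply is that little turns on this. The SAP introduces the provision with "In the unlikely event that a subject starts to consume peanut ad libitum before exiting the trial". Protocol 9.1.1 prespecifies the exception, and it covers both arms. Section 12 has the classification settled and documented by a blinded team before database lock. Footnote [4] may only mean that no 300 mg value is imputed. Because subcategories are tabulated by arm, a reader can rebuild the primary 2×2 table with these subjects as failures.

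Most of this stands as a limit on weight. It does not remove the contradictions. Blinding prevents a choice by arm but does not say which written threshold applies. Section 12 reserves case-by-case imputation for subjects with additional reasons for missing the challenge, so it does not settle a plain one-kernel case. The primary table can be rebuilt from the counts, but the two MTD models cannot be refitted from summary tables.

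A reader might infer more than the documents support:

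- **That the SAP invented a loophole favouring CPNA.** The exception is in the protocol, and a placebo case works against CPNA.
- **That different people would class the same subject differently.** Section 12 provides for one documented team determination.
- **That footnote [4] leaves wide gaps for peanut eaten once or with mild symptoms.** The Table 7.1 row applies only to those who added peanut to their diet, which a single intake hardly meets. SAP 7.3 defines a tolerated challenge dose as one with no more than mild symptoms. The direct threshold conflict is confined to exactly one kernel.
- **That one such subject costs about 9.5 points of power.** That figure (80.0% to 70.5%) subtracts a subject from the design-rate responders, who already exclude the unchallenged.
- **That the kernel standard must give way to a 300 mg amount.** The SAP names the kernel as its target level. A 300 mg threshold would replace that choice, not reconcile the text.

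**Conclusion.** The concern holds as a set of conflicting rules and a missing sensitivity test, and should be fixed. The one-kernel conflict and the footnote's missing MTD are both in the current text, and no planned test counts documented ad libitum subjects as failures.

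Expected impact is small. The probabilities of about 0.07 and 0.10 are conditional on exactly one such subject and on the design rates. The documents give no expected count, so neither figure is an unconditional risk, and the direction depends on the arm. The loss of a non-responder from the MTD analyses requires the footnote to override both 7.3 and 9.3.1. That one kernel falls below the endpoint dose rests on equating a kernel with a whole peanut.

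**What to change.** All changes can be made in the SAP:

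1. Change both ad libitum cells of Table 7.1 to require more than a single peanut kernel, matching 7.3 and footnote [4]. Make Table 7.2 refer to that criterion. In footnote [4], replace the symptom-free condition with 7.3's notion of tolerated (no more than mild symptoms).
2. In footnote [4], replace the statement that no value is imputed with imputation of the screening DBPCFC MTD. Apply it to every ad libitum subject who does not meet the criterion.
3. Add an ITT sensitivity analysis of the primary and both key secondary endpoints. It should count all ad libitum subjects without an exit DBPCFC as non-responders with their screening MTD. This also covers those whose imputation is decided case by case.

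The exception in protocol 9.1.1 stays, and no protocol amendment is needed. The cost is a few wording changes, a few extra tables and a sensitivity result that may move either way: down for a CPNA case, up for a placebo case.
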